**7.1.5. (12-Lead) Electrocardiogram Measurements**

A standard 12-lead (with a 10-second rhythm strip) tracing will be used for all ECG assessments.

All patients require a triplicate ECG measurement at screening. On-treatment ECGs will be performed as outlined in the SOA table. At each time point, 3 consecutive 12-lead ECGs (triplicates) will be performed approximately 2 minutes apart to determine mean QTc (average of triplicates). When coinciding with blood sample draws for PK, ECG assessment (as well as CK and troponin, if clinically indicated) should be performed prior to blood sample collection, such that the blood sample is collected at the nominal time.

Clinically significant findings seen on subsequent ECGs should be recorded as adverse events. In case of QTc >500 msec (ie, CTCAE Grade >2), ECG must be reviewed by qualified personnel at the site as soon as the finding is made, including verifying that the machine reading is accurate and that the Fridericia correction formula is applied. If the manual reading verifies a rate corrected QTc of >500 msec, repeat ECG should be immediately performed at least two times approximately 2 to 4 minutes apart.

An electronic reading of prolonged QTc must be confirmed by manual reading. Prior to conclusion that an episode of prolongation of the QTc interval is due to study drug, thorough consideration should be given to potential precipitating factors (eg, change in patient clinical condition, effect of concurrent medication, electrolyte disturbance) and possible evaluation by specialist. If QTc interval reverts to less than 500 msec, and in the judgment of investigator and sponsor is determined to be due to a cause other than study drug, treatment may be continued with regular ECG monitoring.

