### **Electrocardiograms**

ECG measurements (an average of the triplicate measurements) will be used for the statistical analysis and all data presentations. Any data obtained from ECGs repeated for safety reasons after the nominal time-points will not be averaged along with the preceding triplicates. Interval measurements from repeated ECGs will be included in the outlier analysis (categorical analysis) as individual values obtained at unscheduled time points.

QT intervals will be corrected for heart rate (QTc) using standard correction factors [ie, Fridericia's (default correction), Bazett's, and possibly a study specific factor, as appropriate]. Data will be summarized and listed for QT, HR, RR, PR, QRS, QTc.

Descriptive statistics (n, mean, median, standard deviation, minimum, and maximum) will be used to summarize the absolute corrected QT interval and changes from baseline in corrected QT after treatment. Categorical analysis will be conducted for the maximum change from baseline in corrected QT and the maximum post-baseline corrected QT interval.

Shift tables will be provided for baseline vs worst on treatment corrected QT. Shift tables will also be provided for ECG abnormality at baseline vs. on treatment. Patients experiencing clinically-relevant morphological ECG changes will be summarized (including frequency and percentage).

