The following analyses will be performed for each applicable ECG parameters (RR, PR, QRS, QT, ventricular rate -denoted as HR in what follows-, and QTc) by treatment arm, during the on-treatment period. The denominator to calculate percentages for each category is the number of patients evaluable for the category.

- Pearson correlation between QT and HR, QTc (QTcB, QTcF and, if applicable, QTcP) and HR using individual (non-averaged) baseline assessments
- For each of the ECG parameters (HR, and QT, QTc, QRS, PR intervals), descriptive statistics at baseline, at each post-baseline time point and changes from baseline at each post-baseline time point
- Frequency (number and percentage) of patients with notable ECG values according to the following categories:
 - QT/QTc increase from baseline >30 ms, >60 ms
 - QT/QTc > 450 ms, > 480 ms, > 500 ms
 - HR ≤ 50 bpm and decrease from baseline ≥ 20 bpm
 - HR ≥ 120 bpm and increase from baseline ≥ 20 bpm
 - PR ≥ 220 ms and increase from baseline ≥ 20 ms
 - QRS ≥ 120 ms

Patients with notable ECG interval values and qualitative ECG abnormalities will be listed for each patient and time point and the corresponding notable values and abnormality findings will be included in the listings.

Unscheduled ECG measurements will not be used in computing the descriptive statistics for change from baseline at each post-baseline time point. However, they will be used in the analysis of notable ECG changes and the shift table analysis of notable QT parameters.

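### SAP 6.6.10 has no by-arm table of new qualitative or morphological ECG abnormalities from the ECG data, although Protocol 9.5 plans two

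*Protocol*

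**What the plan says.** Protocol 9.5, under Electrocardiograms, ends with three tabulated outputs:

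- for corrected QT, "Shift tables will be provided for baseline vs worst on treatment corrected QT";
- separately, "Shift tables will also be provided for ECG abnormality at baseline vs. on treatment";
- for morphology, "Patients experiencing clinically-relevant morphological ECG changes will be summarized (including frequency and percentage".

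SAP 6.6.10 opens its list of summaries with "The following analyses will be performed for each applicable ECG parameters" and names RR, PR, QRS, QT, ventricular rate and QTc, by treatment arm. The counts are introduced as "Frequency (number and percentage) of patients with notable ECG values according to the following categories", and every category that follows is numeric. For everything else the section says "Patients with notable ECG interval values and qualitative ECG abnormalities will be listed for each patient and time point". A shift table appears only in the rule on unscheduled ECGs, which says "they will be used in the analysis of notable ECG changes and the shift table analysis of notable QT parameters".

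Protocol 7.1.5 also bears on the point: "Clinically significant findings seen on subsequent ECGs should be recorded as adverse events".

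**The concern.** The protocol treats qualitative ECG findings as something to be counted and compared with baseline. The SAP treats them as something to be read line by line. A listing gives no denominator, no baseline comparison and no contrast between arms.

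This matters more here than in most trials. Protocol 1.2.3 reports a fatal myocarditis with this combination in the Phase 1b study, with an immune-mediated cause confirmed by pathology. Protocol 1.3 sets out regular MUGA or echocardiogram, ECG, BNP, troponin and CK-MB monitoring because of early cardiac cases. Rhythm, ST-T and some conduction-pattern changes can occur without crossing any of the SAP's rate or interval thresholds. The SAP tabulates the other strands of that monitoring: shifts from normal for BNP, troponin and CK-MB (6.6.7.1), and LVEF shifts and decreases (6.6.9). Even physical examination abnormalities get counts by body system (6.6.11). Qualitative ECG is the strand left to a listing.

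**Working it through.** No sample size, power or error rate is involved, so the check is a comparison of the two texts.

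**Step 1. Match each protocol output to the SAP.**

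| Protocol 9.5 output | Counterpart in SAP 6.6.10 |
|---|---|
| Shift table, corrected QT, baseline vs worst on treatment | Mentioned in the unscheduled-ECG rule; not specified in the list of summaries |
| Shift table, ECG abnormality, baseline vs on treatment | None; listing only |
| Number and percentage with clinically relevant morphological changes | None; listing only |

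Two of the three outputs have no counterpart. The protocol introduces the abnormality shift table as an addition to the corrected-QT one, so the QT table cannot stand in for it.

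**Step 2. See what ECG information still reaches a by-arm table.**

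- Interval route (SAP 6.6.10). The counts cover QT/QTc above 450, 480 and 500 ms; QT/QTc increases above 30 and 60 ms; heart rate at or below 50, or at or above 120 bpm, with a change of at least 20 bpm; PR of at least 220 ms with an increase of at least 20 ms; and QRS of at least 120 ms. The QT-increase, heart rate and PR categories require a change from baseline, so they count new findings.
- Adverse event route. Clinically significant ECG findings are to be recorded as adverse events (Protocol 7.1.5). SAP 6.6.1 tabulates treatment-emergent events by arm, system organ class and preferred term. SAP 6.6.4 adds risk differences for immune-related and Tier-2 events. Tier 2 needs at least 10% of patients at any grade, or 5% at Grade 3 to 5, in either arm (SAP 3.5.1).

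**Step 3. Identify what neither route gives.** Neither gives a cross-classification of baseline against on-treatment ECG status, or a single count per arm of patients with a new qualitative finding. Findings that the investigator did not report as adverse events are seen only in the listing.

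**Step 4. Check whether the ECG schedule supports a fair comparison.** Footnote 15 of the Schedule of Activities sets Cycle 1 ECGs on Days 1, 15 and 29. Arm A has them before and at the end of infusion, which is 3 × 2 = 6 time points. Arm B has them before sunitinib intake, which is 3 × 1 = 3. If the Day 1 pre-dose ECG is the baseline (SAP 3.4.1), the post-dose scheduled time points in Cycle 1 number 6 − 1 = 5 in Arm A and 3 − 1 = 2 in Arm B. A worst-on-treatment table built on all of them would give Arm A more chances to show an abnormality. The time points shared after baseline are the pre-dose ECGs on Days 15 and 29 and, where done, the End of Treatment ECG.

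**The case against.** The strongest reply is that little is lost. A morphological change that matters clinically should be recorded as an adverse event and so be counted by arm. Rate and conduction abnormalities are counted from the ECG data. Protocol 9.8 sets up an independent committee to adjudicate selected cardiac events. The scheduled triplicate ECGs are described as a means of determining mean QTc, which fits an interval-based analysis. Both the Protocol (Section 9) and the SAP (Section 2) allow the SAP to change protocol plans, with an amendment needed only for major changes to the primary endpoint or its analysis.

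Much of this stands. A reader might infer that new ECG abnormalities cannot be compared between the arms at all, or that only QTc will be compared. The documents do not support either reading, because of the two routes in Step 2. A reader might also infer that the change was made without any explanation. That cannot be established: the table of major SAP changes named in the SAP's list of tables is not in the text available, so one can say only that 6.6.10 gives no reason.

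The adverse event route is still not a substitute. It depends on investigator judgement in an open-label trial, spreads findings over preferred terms and has no baseline cross-tabulation. From Cycle 2, Day 15 and Day 29 events in the sunitinib arm may be collected by telephone (Protocol 6.2), so later ascertainment differs between arms. The adjudication committee starts from reported adverse events, not from the ECG data.

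**Conclusion.** The discrepancy holds: two by-arm ECG summaries planned in Protocol 9.5 are absent from SAP 6.6.10, and the third is mentioned without being specified. The consequence is moderate and confined to descriptive cardiac safety reporting. Its size cannot be estimated, because the documents give no rate of qualitative ECG abnormality and no share of such findings that would go unreported as adverse events.

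The conclusion assumes that clinically significant findings are in fact recorded as Protocol 7.1.5 asks; if they are not, the loss is larger. It also assumes that the planned listing means qualitative findings are held in the database. Since the SAP may modify the protocol's plans, this is an omission to reconcile, not a breach.

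**What to change.** In SAP 6.6.10 add, by treatment arm on the safety analysis set:

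1. a shift table of ECG abnormality, baseline against worst on treatment;
2. the number and percentage of patients with a new clinically relevant morphological change, by type where the collected data allow.

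Base both on the scheduled time points that the arms share. State this explicitly, because the section's present rule brings unscheduled ECGs into its shift analysis. Keep the listing, which will still show end-of-infusion and unscheduled findings. While the section is open, specify the QT shift table that it now only mentions. If the sponsor prefers not to produce the two tables, the SAP should say that they were dropped and why.

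The cost is two descriptive tables and a working definition of clinically relevant, fixed before the tables are run. The listing already requires the underlying findings. The documents do not show an overall-interpretation field or coding by type, so the breakdown by type is conditional on what was collected.

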### **9.6. Interim Analysis**

The interim and the primary analyses for each endpoint will be performed based on the Full Analysis Set after all patients have been randomized in the study and the target number of events has occurred as described below. A maximum of 4 distinct analyses cutoffs are planned in the study:

- at the time when approximately 235 PFS events (70% of the expected 336 events) by BICR assessment have occurred in the PD-L1+ population (IA for PFS and IA1 for OS);
- at the time when 336 PFS events by BICR assessment have occurred in the PD-L1+ population (primary analysis for PFS and IA2 for OS);
- 15 months after the primary analysis for PFS (IA3 for OS);
- at the time when 368 deaths have occurred in the PD-L1+ population (primary analysis for OS).

Table 9 displays the maximum number of analyses expected for each of the primary endpoints and the associated efficacy and futility boundaries. The futility boundaries are non-binding but the study may be stopped for futility if at the time of the first interim analysis, both PFS and OS in the PD-L1+ population cross the corresponding futility boundaries. If the efficacy boundary is crossed, for either of the primary endpoints, at the time of an interim analysis or at the time of the primary analysis then the primary objective of the study will have been demonstrated.

**Table 9. PFS and OS in the PD-L1+ population – Efficacy and Futility Boundaries**

Endpoint	PFS in PD-L1+		OS in PD-L1 +			
	IA1	PA	IA1	IA2	IA3	PA
Analysis cutoff trigger	235 PFS events in PD-L1+	336 PFS events in PD-L1+	235 PFS events in PD-L1+	336 PFS events in PD-L1+	15 months after IA2	368 deaths in PD-L1+
Number of events (Information fraction)	235 (70%)	336 (100%)	125 (34%)	195 (53%)	294 (80%)	368 (100%)
p-value (z-value) for efficacy	<0.0006 (<-3.2493)	<0.0038 (<-2.6682)	<0.00007 (<-3.7913)	<0.0015 (<-2.9686)	<0.0093 (<-2.3524)	<0.0180 (<-2.0975)
p-value (z-value) for futility a	>0.4059 (>-0.2380)	NA	>0.6411 (>0.3614)	>0.3672 (>-0.3394)	>0.0879 (>-1.3537)	NA
a Non-binding. IA1 = interim analysis 1, IA2 = interim analysis 2, IA3 = interim analysis 3, PA = primary analysis The observed number of events at the IAs may not match the planned number of events. The efficacy and futility boundaries will be updated based on the actual number of observed events using the pre-specified $\alpha$ -and $\beta$ -spending functions.						

Table 10 displays the analyses triggers for PFS and OS in the ‘all comers’ population, as well as the associated efficacy boundaries. As described in [Section 9.1](#), the significance level for the analyses of these endpoints is determined by the closed testing procedure.

**Table 10. PFS and OS in the ‘All Comers’ Population – Efficacy Boundaries**

Endpoint	PFS in ‘All Comers’		OS in ‘All Comers’			
	IA1	PA	IA1	IA2	IA3	PA
Analysis cutoff trigger	235 PFS events in PD-L1+	336 PFS events in PD-L1+	235 PFS events in PD-L1+	336 PFS events in PD-L1+	15 months after IA2	368 deaths in PD-L1+
Number of events a (Information fraction)	343 (70%)	490 (100%)	182 (34%)	283 (53%)	427 (80%)	534 (100%)
p-value (z-value) for efficacy b	<0.0006 (<-3.2478)	<0.0038 (<-2.6683)	<0.00012 (<-3.6656)	<0.0020 (<-2.8726)	<0.0115 (<-2.2727)	<0.0212 (<-2.0286)
a Number of events expected under H 13 for PFS (assuming a HR of 0.7) and H 14 for OS (assuming a HR of 0.75). b The p-values and z-values noted for OS are those associated with the scenario when both H 02 and H 03 are rejected. IA1 = interim analysis 1, IA2 = interim analysis 2, IA3 = interim analysis 3, PA = primary analysis The observed number of events at the IAs may not match the planned number of events. The efficacy and futility boundaries will be updated based on the actual number of observed events using the pre-specified $\alpha$ -spending functions.						

[REDACTED] The efficacy and futility boundaries will be updated based on the actual number of observed events using the pre-specified  $\alpha$ - and  $\beta$ -spending functions. Therefore, the observed Z-test statistic at the interim analysis will be compared with the updated efficacy and futility boundaries. If the study continues to final analysis, the p-value that will be used to declare statistical significance at the final analysis for each endpoint will be based on the actual number of events documented at the cut-off date for the final analysis and the  $\alpha$  already spent at the interim analysis. Further details will be provided in the Statistical Analysis Plan.

If the results of the interim analysis indicate serious safety concerns, the sponsor, in conjunction with an external Data Monitoring Committee (E-DMC), will communicate with the Health Authorities regarding stopping the clinical trial.

**9.7. Data Monitoring Committee**

This study will use an external data monitoring committee (E-DMC).

The E-DMC will be responsible for ongoing monitoring of the safety and efficacy of patients in the study according to the charter. The recommendations made by the E-DMC to alter the conduct of the study will be forwarded to Pfizer for final decision. Pfizer will forward such decisions, which may include summaries of aggregate analyses of endpoint events and of safety data that are not endpoints, to regulatory authorities, as appropriate.

The E-DMC will perform a preliminary review of safety data, without holding of recruitment, for the first 30 patients randomized in a 1:1 ratio and treated in the study, who have been followed for at least 6 weeks each after the first dose. The E-DMC assessment will be conducted based on the available safety data of the first 30 patients and on all the available safety data of other patients treated up to the data cut-off. Subsequently, the E-DMC will convene to monitor safety in the study approximately every 6 months after the first meeting.

Recommendations for study conduct (continue as planned, continue with modifications, terminate) including whether the study has met the pre-specified minimal futility or efficacy criteria will be conveyed to the sponsor by the E-DMC chair.

#### **9.8. Cardiac Events Adjudication Committee**

An independent cardiac events adjudication committee will be established to review selected cardiac adverse events reported in the study in order to confirm the diagnosis and relationship to study treatment, as described in the relevant charter. AEs that will be selected and any other relevant data for this review will be pre-specified in the cardiac events adjudication charter and endorsed by the committee.

### **10. QUALITY CONTROL AND QUALITY ASSURANCE**

Pfizer or its agent will conduct periodic monitoring visits during study conduct to ensure that the protocol and Good Clinical Practices (GCPs) are being followed. The monitors may review source documents to confirm that the data recorded on CRFs is accurate. The investigator and institution will allow Pfizer monitors/auditors or its agents and appropriate regulatory authorities direct access to source documents to perform this verification. This verification may also occur after study completion.

During study conduct and/or after study completion, the study site may be subject to review by the institutional review board (IRB)/ethics committee (EC), and/or to quality assurance audits performed by Pfizer, or companies working with or on behalf of Pfizer, and/or to inspection by appropriate regulatory authorities.

The investigator(s) will notify Pfizer or its agents immediately of any regulatory inspection notification in relation to the study. Furthermore, the investigator will cooperate with Pfizer or its agents to prepare the study site for the inspection and will allow Pfizer or its agent, whenever feasible, to be present during the inspection. The investigator will promptly provide copies of the inspection findings to Pfizer or its agent. Before response submission to the regulatory authorities, the investigator will provide Pfizer or its agents with an opportunity to review and comment on responses to any such findings.

It is important that the investigator(s) and their relevant personnel are available during the monitoring visits and possible audits or inspections and that sufficient time is devoted to the process.

Japan only: After the combination of avelumab with axitinib is approved for treatment of aRCC by MHLW, this study will be conducted according to Good Post Marketing Surveillance Practices (GPSP) in addition to GCP.

These changes are regulatory requirements only applied to Japan. As per Japan regulation, once the investigational drug is approved by MHLW in Japan, the clinical trial should be conducted as a post-marketing clinical study. Consequently, upon approval of the combination of avelumab with axitinib in Japan, references to Study B9991003 using the terms “clinical study” or “clinical trial” mentioned in the protocol will be interpreted as “post-marketing clinical study”.

## **11. DATA HANDLING AND RECORD KEEPING**

### **11.1. Case Report Forms/Electronic Data Record**

As used in this protocol, the term CRF should be understood to refer to either a paper form or an electronic data record or both, depending on the data collection method used in this study.

A CRF is required and should be completed for each included patient. The completed original CRFs are the sole property of Pfizer and should not be made available in any form to third parties, except for authorized representatives of Pfizer or appropriate regulatory authorities, without written permission from Pfizer.

The investigator has ultimate responsibility for the collection and reporting of all clinical, safety and laboratory data entered on the CRFs and any other data collection forms (source documents) and ensuring that they are accurate, authentic/original, attributable, complete, consistent, legible, timely (contemporaneous), enduring and available when required. The CRFs must be signed by the investigator or by an authorized staff member to attest that the data contained on the CRFs are true. Any corrections to entries made in the CRFs or source documents must be dated, initialed and explained (if necessary) and should not obscure the original entry.

In most cases, the source documents are the hospital's or the physician's patient chart. In these cases data collected on the CRFs must match the data in those charts.

In some cases, the CRF, or part of the CRF, may also serve as source documents. In these cases, a document should be available at the investigative site as well as at Pfizer and clearly identify those data that will be recorded in the CRF, and for which the CRF will stand as the source document.

## **11.2. Record Retention**

To enable evaluations and/or audits from regulatory authorities or Pfizer, the investigator agrees to keep records, including the identity of all participating patients (sufficient information to link records, eg, CRFs and hospital records), all original signed informed consent documents, copies of all CRFs, safety reporting forms, source documents, and detailed records of treatment disposition, and adequate documentation of relevant correspondence (eg, letters, meeting minutes, telephone calls reports). The records should be retained by the investigator according to International Conference on Harmonisation (ICH), local regulations, or as specified in the Clinical Study Agreement (CSA), whichever is longer.

If the investigator becomes unable for any reason to continue to retain study records for the required period (eg, retirement, relocation), Pfizer should be prospectively notified. The study records must be transferred to a designee acceptable to Pfizer, such as another investigator, another institution, or to an independent third party arranged by Pfizer. Investigator records must be kept for a minimum of 15 years after completion or discontinuation of the study or for longer if required by applicable local regulations.

The investigator must obtain Pfizer's written permission before disposing of any records, even if retention requirements have been met.

